8.4.5.2 Physical Examination

Perform a physical examination within 24 hours prior to the first LUMASON administration and record any significant changes at 24 hours after the last LUMASON administration on the Adverse Event CRF. The subject's baseline physical examination will be recorded on the Medical/Physical exam section of the CRF.

8.4.5.3 Vital Signs

Collect blood pressure and heart rate at the time points listed below. Obtain all the vital signs in a position that is consistent for all time points for each subject.

Rest echocardiography:	within 1 hour prior to the Rest LUMASON (CEUS) administration 30 minutes after the Rest LUMASON (CEUS) administration
Stress echocardiography:	immediately prior to the Stress LUMASON (CE-DSE) administration 30 minutes after the Stress LUMASON (CE-DSE) administration 1 hour after the Stress LUMASON (CE-DSE) administration* 24 hours after the Stress LUMASON (CE-DSE) administration*

**If stress echocardiography (CE-DSE) is not performed, obtain vitals at 1 and 24 hours after the rest LUMASON administration.*

8.4.5.4 Laboratory Evaluations

Collect blood samples within 24 hours prior to the first LUMASON administration and 24 hours after the last LUMASON administration. A central laboratory will perform evaluations for the analytes listed in Table B:

Table B: Laboratory Analytes

Hematology	Clinical Chemistry		Cardiac Biomarker
Hematocrit	Sodium	AST/SGOT	Cardiac Troponin
Hemoglobin	Potassium	ALT/SGPT	
RBC count	Chloride	Alkaline Phosphatase	
WBC count	Glucose	GGT	
differential WBC count	Urea Nitrogen	Uric Acid	
Platelets	Creatinine	Total Protein	
	Total Bilirubin	Albumin	
	LDH	Calcium	
	Magnesium		

Prepare blood samples and ship via overnight courier per the Instruction Manual provided by the central laboratory.

8.4.5.5 Electrocardiograms

A 12-Lead electrocardiogram (ECG) will be performed in all subjects at the following time points:

Rest echocardiography: within 1 hour prior to the Rest LUMASON (CEUS) administration
30 minutes after the Rest LUMASON (CEUS) administration

Stress echocardiography: immediately prior to the Stress LUMASON (CE-DSE) administration
30 minutes after the Stress LUMASON (CE-DSE) administration
1 hour after the Stress LUMASON (CE-DSE) administration*
24 hours after the Stress LUMASON (CE-DSE) administration*

**If stress echocardiography (CE-DSE) is not performed, obtain ECGs at 1 and 24 hours after the rest LUMASON (CEUS) administration.*

ECG examinations will be evaluated by a central ECG laboratory that will provide the ECG equipment to the site and will employ a cardiologist to perform the centralized ECG evaluation containing the following information:

- RR interval
- PR interval
- QRS interval
- QT and QTc interval (Bazett's and Fridericia's)
- Overall diagnostic assessment
- Comparison to Baseline

Attach a photocopy of the ECG reports to the appropriate page of the CRF. A dual snap electrode will be supplied to the site by the central ECG laboratory in order to allow the acquisition of both discrete (static) 12-lead ECGs and continuous ECG monitoring described in section 8.4.5.6.

8.4.5.6 Continuous Electrocardiograms

Continuous ECG monitoring will be performed starting 10 minutes prior to the first administration of LUMASON (CEUS) and will continue through 30 minutes after the last administration of LUMASON.

Continuous ECG examinations will be evaluated on site by the Investigator.

8.4.5.7 Pulse Oximetry

Pulse oximetry will be monitored starting at 10 minutes prior to the first administration of LUMASON (CEUS) and continuing through 30 minutes after the last LUMASON administration (CE-DSE).

Pulse oximetry will be evaluated by the on-site Investigator.

8.5 Imaging Procedures

At each site, the same commercially available echocardiographic equipment and transducers will be used for all subjects. Subjects will be examined in either the supine or lateral decubitus position. The transmit power (≤ 0.8 MI) and the gain setting will be adjusted at the beginning of each procedure to obtain optimal endocardial visualization. Both settings must be kept constant throughout each subject's evaluation. Focus will be set at the far field below the mitral valve.

Every effort must be made to keep the optimal transducer position for standard views. At each site, image acquisition should be performed by the same sonographer throughout each subject's study. See Figure 1 for the order of imaging procedures.

Both the rest (UEUS and CEUS) and the stress (UE-DSE and CE-DSE) examinations must be identified by subject number and stored as DICOM clips for transfer to the central imaging lab according to the instructions in the provided Imaging Manual. The investigational sites are also required to maintain a copy of the subject's examination as a record of the study.

Prior to rest administration of LUMASON (CEUS), further evaluation for intracardiac shunt will be demonstrated with agitated saline study to assess the interatrial septum, unless an intracardiac shunt has been previously ruled out. If no evidence of intracardiac shunt is confirmed by the cardiologist, the subject will further undergo a CEUS echocardiography examination.

8.5.1 Rest Echocardiography

At rest, UEUS will be acquired using harmonic imaging with the standard apical 4-, 2-, and 3-chamber views. Following the rest UEUS echocardiogram, a rest CEUS echocardiogram will be performed with administration of a single 2 mL bolus injection of LUMASON. A recording of 2D transthoracic harmonic echocardiography imaging will be performed from 30 seconds prior to injection of LUMASON and continue until all images are acquired. For the rest CEUS images,

the apical 4-chamber view will be acquired first followed by the apical 2- and 3-chamber views.

8.5.2 Pharmacologic Stress with Dobutamine

For stress, dobutamine will be administered intravenously by infusion pump at least 30 minutes after the rest LUMASON administration starting at a rate of 5 µg/kg/min. At 3 minute intervals, the infusion rate can be increased to 10, 20, 30, and 40 µg/kg/min to reach one of the following peak stress endpoints:

[figure not shown]
- Target heart rate: $0.85 \times (220 - \text{age})$;
- Development of new or worsening regional wall motion abnormalities;
- Peak dose;
- Significant arrhythmias;
- Severe hypertension (systolic blood pressure >200 mmHg or diastolic blood pressure >110 mmHg);
- Hemodynamically significant hypotension;
- Intolerable symptoms.

If a peak stress endpoint is reached, the test can be stopped before reaching the maximal dose of dobutamine. If no peak stress endpoint is reached after the maximum dose of dobutamine, 0.25 mg to 0.5 mg of atropine can be administered intravenously at peak infusion to increase heart rate. If peak stress is still not reached, atropine, in divided doses of 0.25 to 0.5 mg up to a total of 2.0 mg, should be used as needed to achieve target heart rate.

8.5.3 Stress Echocardiography

Immediately after the administration of dobutamine, with or without the addition of atropine, a stress UE-DSE echocardiogram will be acquired at peak stress using harmonic imaging with the standard apical 4-, 2-, and 3-chamber views. Following the stress UE-DSE echocardiogram, a stress CE-DSE echocardiogram will be performed with administration of a single 2 mL bolus injection of LUMASON. A recording of 2D transthoracic harmonic echocardiography imaging will be performed from 30 seconds prior to injection of LUMASON and continue until all images are acquired. For both US-DSE and CE-DSE images, the apical 4-chamber view will be acquired first followed by the apical 2- and 3-chamber views.

Figure 1: Imaging Procedures

8.6 Efficacy Evaluations

8.6.1 On-Site

The on-site Investigators will provide an overall diagnosis of CAD (Section 8.6.3.3) for each subject based on wall motion abnormalities from the results of the unenhanced (UEUS & UE-DSE) and contrast-enhanced (CEUS and CE-DSE) echocardiographic images.

8.6.2 Off-Site

The off-site efficacy evaluations of the echocardiographic images will be performed by 3 independent, experienced readers, unaffiliated with the investigational sites and blinded to any clinical information for subjects enrolled in this study. These off-site blinded readers will score EBD (Section 8.6.3.1), LV wall motion (Section 8.6.3.2) and overall diagnostic conclusion (Section 8.6.3.3).

[figure not shown]
8.6.3 Efficacy Measurements

If the subject does not complete the echocardiography examinations (rest, stress or any views are missing) the subject will not be included in the efficacy evaluation for on- or off-site.

8.6.3.1 Endocardial Border Delineation

The assessment of EBD will be performed by dividing the heart into 17 segments using the standard apical 4-, 2-, and 3-chamber views (see Figure 2) according to the ASE^{1,12,27} guidelines:

Figure 2: 17-Segment Model

LV EBD will be graded for each segment of the 17-segment model shown in Figure 2 by each off-site reader using the following 3-point scale:

- 0 = Inadequate (endocardial border not visible)
- 1 = Sufficient (endocardial border barely visible)
- 2 = Good (endocardial border clearly visible)

For LV EBD, separate assessments will be collected for the unenhanced (UE-DSE) and contrast-enhanced (CE-DSE) images at peak stress.

8.6.3.2 LV Wall Motion

LV wall motion will be graded by each off-site reader using the following 3-point scale at rest and peak stress for unenhanced (UEUS and UE-DSE) and contrast-enhanced (CEUS and CE-DSE) images:

- 1 = Normal
- 2 = Abnormal (Mild-Moderate, Severe Hypokinesis, Akinetic and/or Dyskinetic)
- 3 = Unevaluable

8.6.3.3 Overall Diagnostic Conclusion

The overall diagnostic conclusion will be determined by the on-site Investigator and the off-site reader using the scoring system in Table C:

1 = Normal

2 = Abnormal (Mild-Moderate, Severe Hypokinesis, Akinetic and/or Dyskinetic)

3 = Unevaluable (Inadequate visualization of segments comprising all coronary artery territories due to motion artifacts, lateral wall drop out, swirling or attenuation artifacts)

Table C: Overall Diagnostic Conclusion Based on LV Wall Motion

Rest	Stress	Overall Diagnostic Conclusion
1 Normal	1 Normal	Normal
1 Normal	2 Abnormal	Abnormal
2 Abnormal	2 Abnormal (no change or worsening)	Abnormal
3 Unevaluable	3 Unevaluable	Unevaluable*

**A score of 3 – unevaluable at either rest or stress will result in an overall diagnostic conclusion of unevaluable.*

Separate assessments will be collected for unenhanced (UEUS and UE-DSE) and contrast-enhanced (CEUS and CE-DSE).

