Stress echocardiography is an established imaging modality for the detection of coronary artery disease (CAD).^{1,2,3,4,5,6,7} The primary indication for conventional stress echocardiography is to indirectly detect angiographically significant ($\geq 50\%$ diameter) stenoses by inducing ischemia or to assess the patient's risk for a cardiac event.^{5,8,9,10} Increasingly stress echo techniques have been shown to offer valuable prognostic information in the risk evaluation of stable chronic CAD.^{5,10,11} Significant studies (> 100 patients) of dobutamine stress echocardiography (DSE) show a range for sensitivity of between 61–95%, while that for specificity ranged from 51–95%¹¹ for the diagnosis of CAD.¹ The detection of CAD with stress echocardiography is based on the observation of contractile dysfunction in any myocardial segment at rest or with stress; therefore, complete visualization of all left ventricular (LV) endocardial borders (EB) is necessary to document or exclude abnormalities of regional myocardial wall thickening confidently.^{12,13} Interpretation of wall thickening is qualitative, highly dependent on the skill and experience of the reviewing physician, and is affected considerably by quality of endocardial border delineation (EBD).^{12,13} Numerous patient factors may produce suboptimal images with poor EBD. Given, in addition, the challenges imposed by excessive cardiac motion due to hyperventilation and tachycardia at peak stress, non-diagnostic or poor-quality images may occur in up to 30% of patients.^{12,13} The advent of digital side-by-side analysis, standardized reporting criteria, and generalized use of tissue harmonic imaging has reduced, but not overcome, this problem.¹²

Use of ultrasound contrast agents (UCAs) has shown to improve EBD during stress echocardiography and is recommended for use in patients with poor unenhanced image quality by both the American Society of Echocardiography (ASE) and the European Association of Echocardiography (EAE).^{12,13} However, while Lumason™ (sulfur hexafluoride lipid-type A microspheres) with an approved trade name in the USA/SonoVue® (sulfur hexafluoride microbubbles) with an approved trade name for everywhere else in the world referred to hereafter as LUMASON, is approved for use in echocardiography both at rest and stress in the

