The muscle and cavity of the LV will be divided into 17 segments (17-segment model). The 17-segment model will be utilized as recommended by the ASE guidelines.^{1,12,27} The standard views of a 2D echocardiogram as defined by the ASE are all used as part of a 2D echocardiogram at rest and stress.²⁶ The clinical utility of improvement in LV EBD resulting from opacification of the LV as an aid in determination of more clinically relevant parameters is recognized by the 2008 ASE consensus statement as leading to improvement in feasibility, accuracy, and reproducibility of echocardiography for the qualitative and quantitative assessment of LV structure and function.¹²

Unevaluable image are defined as images with inadequate visualization of segments comprising all coronary artery territories due to 1 or more of the following artifacts: motion artifacts, lateral wall drop out, swirling or attenuation artifacts. From the published literature⁶ and previous Bracco-sponsored study²⁵ 8% of the UE-DSE images are expected to be unevaluable.

Stress can be induced by either physical exercise or pharmacologic agents. Physical stress was the first reported and used form of stress echocardiography, but it has several disadvantages since during exercise it is not possible to perform close echocardiographic monitoring and recordings are not reliable because of hyperventilation. Pharmacologic stress overcomes these disadvantages.

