5.4.1 Inclusion Criteria

Enroll a subject in this study if the subject meets the following inclusion criteria:

- Provides written Informed Consent and is willing to comply with protocol requirements;
- Is at least 18 years of age;
- Has suspected or known CAD and is scheduled to undergo coronary angiography within 6 months after the LUMASON DSE.
- Has undergone a previous echocardiography prior to enrollment; resulting in suboptimal unenhanced images at rest, defined as ≥ 2 suboptimal adjacent segments in any apical view.

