10.6.1.2 Evaluation of CAD

The overall diagnostic echocardiographic conclusion will be classified by the off-site readers as Normal, Abnormal or Unevaluable for unenhanced (UEUS and UE-DSE) and LUMASON-enhanced (CEUS and CE-DSE) echocardiography respectively.

The diagnostic performance of echocardiography (UE-DSE and CE-DSE) will be derived based on the diagnosis from stress echocardiography and diagnosis from truth standard (see Table E).

Table E: Cross Tabulation of Diagnosis: Truth Standard vs. Stress Echocardiography

Truth Standard (TS)	Stress Echocardiography		
	Normal	Unevaluable*	Abnormal
Negative	TN	FP	FP
Positive	FN	FN	TP

TN = true negative; TP = true positive; FN = false negative; FP = false positive

*Unevaluable is defined as: inadequate visualization of segments comprising all coronary artery territories due to motion artifacts, lateral wall drop out, swirling or attenuation artifacts.

The null hypothesis is that there is no difference in sensitivity/specificity between CE-DSE and UE-DSE at peak stress; the alternative hypothesis is that CE-DSE is superior to UE-DSE in terms of higher sensitivity/specificity:

$$H_0: \text{Diag}_{\text{CE}} - \text{Diag}_{\text{UE}} = 0,$$

$$H_a: \text{Diag}_{\text{CE}} - \text{Diag}_{\text{UE}} > 0;$$

where Diag_{CE} and Diag_{UE} denote sensitivity/specificity for CE-DSE and UE-DSE at peak stress respectively.

The sensitivity and the specificity along with their 95% confidence intervals (CIs) will be calculated, and the difference in sensitivity/specificity will be tested using McNemar's Chi-square 2-sided test.

In addition, inter-reader agreement for the detection/exclusion of CAD for CE-DSE and UE-DSE will be evaluated by kappa statistic.

10.6.2 Co-Primary Efficacy Endpoint – Critical Shift of Subjects with Suboptimal Images to Adequate Images

The co-primary endpoint: The proportion of subjects with suboptimal images (≥ 2 adjacent segments with inadequate LV EBD in any of the 3 apical views) at UE-DSE converted to adequate images (reduction of suboptimal adjacent segments to obtain adequate images) at CE-DSE will be estimated along with the 95% CIs.

Additionally, the following supportive analyses will be performed:

- proportion of subjects with optimal images at UE-DSE to suboptimal (≥ 2 adjacent segments with inadequate LV EBD in any of the 3 apical views) at CE-DSE in terms of LV EBD visualization will be estimated along with the 95% CIs.

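### The Table C footnote turns a stress-Abnormal read into Unevaluable when the rest image is unreadable, and Table E then counts it as a missed case in CAD-positive subjects

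*Combined protocol and SAP*

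**What the plan says.** Section 8.6.3.2 has each off-site reader score wall motion as Normal, Abnormal or Unevaluable, at rest and at peak stress, for unenhanced and for contrast-enhanced images. Section 8.6.3.3 combines the two phases in Table C. Two of its rows concern an Abnormal stress score: "1 Normal 2 Abnormal Abnormal" (rest Normal) and, for rest Abnormal, "2 Abnormal (no change or worsening) Abnormal". The footnote adds that a score of "unevaluable at either rest or stress will result in an overall diagnostic conclusion of unevaluable", with no exception when the other phase is Abnormal.

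Section 10.6.1.2 states that "The diagnostic performance of echocardiography (UE-DSE and CE-DSE) will be derived based on the diagnosis from stress echocardiography" and the truth standard. For CAD-positive subjects the Table E row, in the order Normal, Unevaluable, Abnormal, reads "Positive FN FN TP". For CAD-negative subjects, Unevaluable and Abnormal are both false positives. Sections 10.6.1 to 10.6.4 contain no alternative coding of Unevaluable.

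The only expected unevaluable rate is in section 5.2: "8% of the UE-DSE images are expected to be unevaluable". No rate is given for the unenhanced rest images (UEUS), the enhanced rest images (CEUS) or the enhanced stress images (CE-DSE).

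**The concern.** Table C reaches Abnormal for an Abnormal stress score with either readable rest score. An unreadable rest image should then rarely matter to the conclusion, yet the footnote lets it cancel the positive finding. In a CAD-positive subject, a reader who recorded the abnormality is entered as having missed the disease.

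The first co-primary endpoint compares sensitivity between the two modalities by McNemar's test in about 45 CAD-positive subjects, reader by reader. One or two reclassified reads per reader can affect the result. The trial rests on contrast making images easier to read, so the combination may well arise more often in the unenhanced set. Counting unevaluable reads as errors looks strict, but in a superiority comparison it is not conservative when it falls more on the comparator.

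**Working it through.** **Step 1: follow the scores through Tables C and E.**

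| Rest | Stress | Overall (Table C and footnote) | Truth positive | Truth negative |
|---|---|---|---|---|
| Normal | Abnormal | Abnormal | TP | FP |
| Abnormal | Abnormal, unchanged or worse | Abnormal | TP | FP |
| Unevaluable | Abnormal | Unevaluable | **FN** | FP |
| Abnormal | Unevaluable | Unevaluable | FN | FP |

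The third line is the point at issue. Scoring it Abnormal changes FN to TP when truth is positive and leaves FP as FP when truth is negative. Sensitivity can only rise and specificity cannot move.

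**Step 2: reproduce the planned sample size.** From section 10.7: difference d = 0.25, discordant proportion ψ = 0.40, two-sided alpha 0.05, power 0.80. Miettinen's formula for the McNemar test is

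n = [1.96ψ + 0.842·√(ψ² − d²(3 + ψ)/4)]² / (ψd²) = 44.87, rounded up to 45.

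This matches the plan.

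**Step 3: discordant cells.** Let p10 be the proportion positive on contrast only and p01 the proportion positive on unenhanced only. Then p10 − p01 = 0.25 and p10 + p01 = 0.40, so p10 = 0.325 and p01 = 0.075. Enumerating the uncorrected McNemar chi-square at n = 45, and summing the probability of every table with p ≤ 0.05 in favour of contrast, gives power 80.4%.

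**Step 4: restore j unenhanced reads.** Assumptions, none of them documented: the 25-point difference is the one seen under the footnote coding; only unenhanced reads are restored; every restored subject is a contrast true positive. Then p10 = 0.325 − j/45 and p01 is unchanged.

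| Restored (j) | p10 | Difference | Power at n = 45 |
|---|---|---|---|
| 0 | 0.325 | 25.0 points | 80.4% |
| 1 | 0.303 | 22.8 points | 74.2% |
| 2 | 0.281 | 20.6 points | 66.8% |
| 3 | 0.258 | 18.3 points | 58.5% |

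A made-up dataset shows the same sensitivity. With 13 against 4 discordant pairs, chi-square = 9²/17 = 4.76 (p = 0.029). With two pairs restored it is 11 against 4, and chi-square = 7²/15 = 3.27 (p = 0.071).

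**Step 5: the reverse case.** Suppose there is no true difference, with 7.5% to 20% of subjects discordant in each direction, and the coding adds contrast-only positives by removing unenhanced true positives. The chance per reader of declaring contrast superior on sensitivity is about 2.3–2.6% with no such loss. It becomes 4.0–4.5% if 2% of CAD-positive subjects are affected and 6.2–7.7% if 4% are.

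**Step 6: equal effect.** If the enhanced reads lose the same share of true positives, the net change in the difference is zero.

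**The case against.** The strongest reply is that requiring both phases to be readable is a coherent, prespecified rule, written identically for both modalities. Section 8.6.3 likewise drops subjects with a missing phase or view. Making an unreadable examination readable is part of what contrast is meant to do, so a gain through evaluability is not simply an artefact. The coding also lowers enhanced sensitivity against the 50% lower-limit criterion. All of this stands for a study in which nothing was found. It does not justify discarding a recorded abnormality.

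A second reply is that Table C's rest-Abnormal row requires the stress abnormality to be unchanged or worse, which needs a readable rest image. This stands in part: a segment that improves but remains abnormal at stress has no row. Every stress-Abnormal pattern that does have a readable-rest row ends in Abnormal.

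Three stronger readings are tempting, and the documents do not support them:

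- *That rest Abnormal with stress Unevaluable is equally wrong.* The Introduction (section 3) says "The detection of CAD with stress echocardiography is based on the observation of contractile dysfunction in any myocardial segment at rest or with stress", but that is background. Table C has no row for rest Abnormal with stress Normal, and the hypotheses concern peak stress.
- *That the 8% rate sizes the problem.* It would give 0.08 × 45 = 3.6 subjects, but it concerns unenhanced stress images and so belongs to the combination just described. The rest-Unevaluable combination has no documented rate.
- *That the entry criterion shows unenhanced rest images will often be unevaluable.* Subjects enter after an earlier examination "resulting in suboptimal unenhanced images at rest", meaning at least two adjacent segments in any one apical view. Unevaluable requires poor visualization across all coronary territories, a much higher bar.

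Sections 8.6.5 and 10.8 defer detail to an off-site methodology document and to the SAP, so a further rule there cannot be excluded.

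**Conclusion.** The point holds for one combination: rest Unevaluable with stress Abnormal. The footnote and Table E together count that read as a false negative in a CAD-positive subject, against the direction of Table C's own rows. The effect is on sensitivity alone.

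A bias towards contrast is a plausible inference from the trial's premise, not a documented fact. It requires such reads, with an Abnormal stress score, to be more frequent in unenhanced images. The number affected is unknown and may be close to zero, and the plan does not say whether its 25-point difference already includes this coding. The fall in power from 80% to 74%, 67% or 59% is therefore a conditional illustration, not an estimate. It shows that a few reads could matter to a co-primary success criterion, which is enough to warrant a low-cost correction.

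**What to change.** Amend the Table C footnote so that a rest score of Unevaluable with a stress score of Abnormal gives an overall conclusion of Abnormal, applied identically to unenhanced and enhanced reads. Report the current footnote coding as a sensitivity analysis. If the primary rule is kept, at minimum prespecify the recoded version as a sensitivity analysis of the sensitivity comparison. In either case tabulate, by reader and modality, how often each rest-by-stress combination occurs in CAD-positive subjects.

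Treat rest Abnormal with stress Unevaluable only as an additional sensitivity analysis, because Table C does not settle it.

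The cost is one line in Table C and the matching derivation in the SAP and reader instructions. Both phase scores are already collected, so no new data are needed. The expected sensitivity gain may be slightly smaller.
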